1.3 Schedule of Activities

Table 1 Schedule of Activities

	Screening period	Treatment period						Follow-up	Section in the CSP
		Randomisation	Visits						
Visit number	1	2	3	4	5	6 ^a	7		
Week	-3	0	1	2	3	6	8		
Study day	-21 to -7 ^a	1	8	15	22	43	57		
Visit window (days)			± 3	± 3	± 3	± 5	± 3		
Informed consent	X								Appendix A 3
Inclusion/exclusion criteria	X	X							Section 5.1 and Section 5.2
Alcohol breath test	X	X				X			Section 5.2
Screen for drugs of abuse	X								Section 8.3.5
AUDIT questionnaire	X								Section 8.3.6.2
Enrolment in IRT/RTSM	X								Section 6.3
Randomisation in IRT/RTSM		X							Section 6.3
Routine clinical procedures									
Demography and baseline characteristics (including smoking history and alcohol consumption)	X								Section 5.3.2

Table 1 Schedule of Activities

	Screening period	Treatment period						Follow-up	Section in the CSP
		Randomisation	Visits						
Visit number	1	2	3	4	5	6 ^a	7		
Week	-3	0	1	2	3	6	8		
Study day	-21 to -7 ^a	1	8	15	22	43	57		
Visit window (days)			± 3	± 3	± 3	± 5	± 3		
Medical/surgical history	X								
Concomitant medication	X	X	X	X	X	X	X	Section 6.9	
Body weight	X	X	X	X	X	X	X	Section 8.2.1.2	
Height, BMI calculation	X							Section 8.3.1	
ECHO	X ^c							Section 8.3.4	
HIV serology	X							Section 8.3.5	
FSH (females only)	X ^d							Section 8.3.5	
Pregnancy tests (females only; serum)	X							Section 8.3.5	
Study intervention									
Study intervention dispensed		X			X			Section 6	
Study intervention accountability (counting remaining tablets and capsules)			X	X	X	X		Section 6.2	

Table 1 Schedule of Activities

	Screening period	Treatment period						Follow-up	Section in the CSP
		Randomisation		Visits					
Visit number	1	2	3	4	5	6 ^a	7		
Week	-3	0	1	2	3	6	8		
Study day	-21 to -7 ^a	1	8	15	22	43	57		
Visit window (days)			± 3	± 3	± 3	± 5	± 3		
Study intervention intake ^a		X	X	X	X	X			Section 6
Key assessments									
Daily digital body weight measurement		Daily home measurement using a digital device should begin at Visit 2 (randomisation) to end of follow-up ^a .							Section 8.2.1.2
Bioimpedance spectroscopy ^a	X	X	X	X	X	X	X		Section 8.2.1.3
Safety assessments									
AE review ^b	X SAEs only	X	X	X	X	X	X		Section 8.4.2
Physical examination	X	X	X ^b	X ^b	X ^b	X ^b	X		Section 8.3.1
ECG central monitoring ^b	X	X (pre-dose) X (2 hours post-dose)	X	X	X	X	X		Section 8.3.3

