Vital signs (supine and standing blood pressure and pulse)	X	X (pre-dose) X (60, 120, 180 minutes)	X	X	X	X	X		Section 8.3.2
Body temperature	X	X	X	X	X	X	X		Section 8.3.2

Table 1 Schedule of Activities

	Screening period	Treatment period						Follow-up	Section in the CSP
		Randomisation	Visits						
Visit number	1	2	3	4	5	6 ^a	7		
Week	-3	0	1	2	3	6	8		
Study day	-21 to -7 ^a	1	8	15	22	43	57		
Visit window (days)			± 3	± 3	± 3	± 5	± 3		
Clinical safety laboratory tests (haematology, clinical chemistry, coagulation, electrolytes, serum osmolality, and NT-pro BNP)	X	X ⁱ	X ⁱ	X ⁱ	X ⁱ	X ⁱ	X	Section 8.3.5	
PK assessments									
Pre-dose PK plasma sample (all participants) ^j			X ⁱ	X ⁱ	X ⁱ			Section 8.5	
PK profile (Japanese)					X ^{k,1}			Section 8.5	
Post-dose sample (Non-Japanese)					X ^m			Section 8.5	

Table 1 Schedule of Activities

	Screening period	Treatment period						Follow-up	Section in the CSP
		Randomisation	Visits						
Visit number	1	2	3	4	5	6 ^a	7		
Week	-3	0	1	2	3	6	8		
Study day	-21 to -7 ^a	1	8	15	22	43	57		
Visit window (days)			± 3	± 3	± 3	± 5	± 3		
Exploratory assessments									
CCI	X ^g					X ^{fg}			Section 8.2.2.1
eGFR calculation ^a	X	X	X	X	X	X	X		Section 8.2.2.2
MELD score calculation	X	X	X	X	X	X	X		Section 8.2.2.3
Child-Pugh score	X	X	X	X	X	X	X		
Non-fasting plasma/serum biomarkers		X ⁱ			X ⁱ	X ⁱ			
HbA1c	X ⁱ	X ⁱ			X ⁱ	X ⁱ			
PROs: CLDQ, PGIS - Liver Disease, and SF-36v2 acute		X ^o				X			Section 8.2.2.4
Collect and store serum and plasma samples for exploratory assessment of biomarkers		X ⁱ				X ⁱ			Section 8.8.1

Table 1 Schedule of Activities

	Screening period	Treatment period						Follow-up	Section in the CSP
		Randomisation	Visits						
Visit number	1	2	3	4	5	6 ^a	7		
Week	-3	0	1	2	3	6	8		
Study day	-21 to -7 ^a	1	8	15	22	43	57		
Visit window (days)			± 3	± 3	± 3	± 5	± 3		
Collect and store urine samples for exploratory assessment of biomarkers		X ⁱ				X ⁱ			Section 8.8.1
Optional Genomics Initiative, exploratory genomics, and multi-omics samples		X							Section 8.7 and Appendix D

- Screening visit can take place from 21 days up to 7 days before randomisation visit (Visit 2). It must be at least 7 days between Visit 1 and Visit 2 to allow time for laboratory results to be examined.
- Brief physical examination.
- Only in those participants with history of Heart Failure and if historical data from ECHO or cardiac MRI in the prior 12 months is not available.

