4 STUDY DESIGN

4.1 Overall Design

This is a Phase IIb multicentre, randomised, double-blind, parallel-group, placebo-controlled study to evaluate the safety of zibotentan/dapagliflozin in combination as compared to zibotentan monotherapy as well as zibotentan/dapagliflozin and zibotentan monotherapy as compared to placebo in patients with cirrhosis. Eligible participants should have a history of decompensation events or compensated cirrhosis with signs of CSPH. If compensated cirrhosis, the eligible participant must have signs and measures that would indicate that the participant has CSPH and includes, but not limited to, presence of gastro-oesophageal varices at endoscopy or collaterals at imaging (either one within 12 months prior to screening), and/or **CCI** [redacted] kPa, or of **CCI** [redacted] kPa with **CCI** [redacted] (at time of screening). Participants should have a MELD score < 15 and should be classified as Child-Pugh A or B ([Table 6](#)).

It is planned that approximately 22 eligible participants will be randomised to each of the 3 treatment groups, for a total of up to 66 participants (see [Figure 1](#)). For details of the study assessments, please see SoA ([Table 1](#)).

This study will consist of the following periods:

Screening Period of up to 3 weeks: The Screening Visit (Visit 1) will take place between 7 to 21 days before the Randomisation Visit (Visit 2) to confirm participant eligibility and collect baseline data. There must be at least 7 days between Visit 1 and Visit 2 to allow sufficient time for laboratory results to be examined. At the Randomisation Visit (Visit 2), eligibility criteria will be reassessed, safety laboratory data reverified, and participants will be provided digital devices to measure their body weight starting the first day after the Randomisation Visit and every day at home.

Treatment Period of 6 weeks: During the Treatment Period, participants will visit the study centre 5 times. At Visit 2, participants will be randomised and will receive the first dose of the study intervention. At each study visit during the treatment period (from Visit 2 till Visit 6) participants will receive the once daily dose at the study centre and will provide a pre-dose blood sample for PK analysis and other lab samples before the intake of study intervention. When not visiting the study centre the patients will take the once daily dose of study intervention at home.

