8.3.2 Vital Signs

Vital signs assessments will be performed at timepoint as specified in the SoA ([Table 1](#)).

Vital signs will include supine and standing blood pressure, pulse, and body temperature measurements.

Routine blood pressure, pulse, and body temperature will be assessed at the study centre, as outlined in the SoA ([Table 1](#)), prior to blood collection for laboratory tests with the participant resting in a supine position using a completely automated device. Manual techniques will be used only if an automated device is not available.

Participants who suffer from **CCI** [REDACTED] and/or **CCI** [REDACTED] of **CCI** [REDACTED] during the course of the study, will be provided with **CCI** [REDACTED]

(Sections 6.1.2 and 8.4.6).

Vital sign measurements in a supine position should be preceded by at least 5 minutes of rest for the participant in a quiet setting without distractions (eg, television, cell phones) and will consist of one pulse, one body temperature, and 3 blood pressure measurements

(3 consecutive blood pressure readings will be recorded at intervals of at least 1 minute). The average of the 3 blood pressure readings will be recorded on the eCRF. In addition, CCI

CCI should be CCI in the CCI.

These assessments should preferably be done in the morning. If CCI is confirmed during the test, it should be reported as an AESI including symptoms related to the measurement of CCI if present (Section 8.4.6).

For information on how AEs based on vital sign results should be recorded and reported, see Section 8.4.4.

Body weight will be measured at the study centre at study visits. There will be safety monitoring of body weight from the home-based monitoring devices, or as an alternative, paper diaries can be used for capturing the information. A body weight change of CCI kg per CCI is regarded as a CCI weight change and needs to be followed up by the investigator.

The investigator will have direct access to the online data for their participants using digital devices. If there is a significant weight gain, the investigator will contact the participant immediately and arrange a clinic visit to assess health status. Participants with paper diaries will be instructed to contact the study staff if there is a significant weight gain.

Participants will also be advised to self-monitor and contact the investigator with any concerns.

8.3.3 **Electrocardiograms**

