9.4.3.4 Electrocardiograms

Electrocardiogram findings will be listed for each participant and will include the ECG parameters (where applicable) and changes from baseline, assessment by the investigator (normal/abnormal not clinically significant/abnormal clinically significant) and details of any

abnormalities. ECG parameters will be summarised by time-point including changes from baseline. The baseline for the safety ECG parameters will be the results obtained pre-dose on Day 1.

ECG parameters to be tabulated will be provided in the SAP.

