3.3.1 General Study Level Definitions

3.3.1.1 Baseline

For alanine aminotransferase (ALT), aspartate aminotransferase (AST), total bilirubin, direct bilirubin, alkaline phosphatase (ALP) and international normalized ratio (INR) baseline is defined as the mean of the values obtained during the screening period including unscheduled visits and the day of first dose.

For ECG and vital signs, baseline is defined as the last non-missing value prior to first administration of dose i.e. post-dose assessment on the day of first administration is not to be used.

The baseline value will for all other data be defined as the last non-missing value prior to or on the same date as administration of the first dose, unless values on the same date are known to be both pre- and post-dose assessments in which case the pre-dose assessment will be used as baseline.

For Loop diuretic baseline definition see section [3.3.1.5](#).

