3.3.2 Visit Window

For the purpose of analysing visit based data, analysis visit windows will be used and are based on first dose date. All scheduled and unscheduled visits occurring the day after first dose or later (including Early Termination visit), will be mapped to an appropriate visit. Unless specified otherwise visit based analyses will follow as shown in [Table 4](#).

Table 4 General visit windowing

Analysis visit label	Analysis visit window start day (day included) ^a	Analysis visit window end day (day included) ^a	Target Day ^a
Week 1	Day 2	Day 11	Day 8
Week 2	Day 12	Day 18	Day 15
Week 3	Day 19	Day 31	Day 22
Week 6	Day 32	Day 50	Day 43
Week 8	Day 51	Day 78	Day 57

a Relative to the date of first dose of study treatment.

For general visit based-summaries, if there is more than one value per subject within a visit window, the closest assessment to the target date is assigned, or the earliest in the event the values are equidistant from the nominal visit date.

Composite endpoints (key objective 1,2,7 and 8) will follow [Table 5](#).

Table 5 Composite endpoints visit windowing

Analysis visit label	Analysis visit window start day (day included) ^a	Analysis visit window end day (day included) ^a
Week 1	Day 1 for component of fluid retention AEs Day 2 for other components	Day 11
Week 2	Day 12	Day 18
Week 3	Day 19	Day 25
Week 6	Day 26	Day 48
Week 8	Day 49	Each subjects EOS ^b

a Relative to the date of first dose of study treatment.

b Given that EOS occurs on or after study day 49.

Data that has been collected daily (loop-diuretic and home weight) will be summarized using visit windowing presented in [Table 6](#).

Table 6 Home weight and Loop-diuretic visit windowing

Analysis visit label	Analysis visit window start day (day included) ^a	Analysis visit window end day (day included) ^a
Week 1	Day 2	Day 8
Week 2	Day 9	Day 15

Analysis visit label	Analysis visit window start day (day included) ^a	Analysis visit window end day (day included) ^a
Week 3	Day 16	Day 22
Week 4	Day 23	Day 29
Week 5	Day 30	Day 36
Week 6	Day 37	Day 43
Week 8	Day 44	Each subjects EOS ^b

a Relative to the date of first dose of study treatment.

b Given that EOS occurs on or after study day 49.

In general, for summaries of extreme data at a subject level, all observations will be included regardless of whether it is included in the by-visit data presentation, e.g. when deriving a statistic such as the maximum.

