4.6.6.2 Presentations

Vital sign parameters will be presented for each treatment group. Vital signs for scheduled post-baseline visits will be presented descriptively for observed values and change from baseline.

Vital sign shift from baseline to maximum will be presented by treatment group.

Treatment emergent vital signs will be presented by treatment group.

Supportive vital sign listings cover observed values and changes from baseline as well as abnormalities.

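### The SAP gives the Day 1 post-dose vital signs (60, 120, 180 minutes) and the 2-hour ECG no analysis time-point in its by-visit vital-sign and ECG-parameter tables

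*SAP*

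**What the plan says.** **Collection.** In the protocol's schedule of activities (1.3), the Visit 2 vital-signs cell, covering supine and standing blood pressure and pulse, has a pre-dose entry followed by "X (60, 120, 180 minutes". The Visit 2 ECG cell has a pre-dose entry followed by "X (2 hours post-dose".

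**Baseline.** For ECG and vital signs, SAP 3.3.1.1 uses the last value before the first dose and adds that a "post-dose assessment on the day of first administration is not to be used".

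**Windows.** SAP 3.3.2 states: "All scheduled and unscheduled visits occurring the day after first dose or later (including Early Termination visit), will be mapped to an appropriate visit". Table 4, the default for visit-based analyses, opens with Week 1 at Day 2 to Day 11. SAP 3.3.1.3 makes the day of first dose Day 1. For subject-level extremes, SAP 3.3.2 uses all observations, whether or not they appear in the by-visit presentation.

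**Presentation.** SAP 4.6.6.2: "Vital signs for scheduled post-baseline visits will be presented descriptively for observed values and change from baseline". SAP 4.6.7.2 tabulates ECG parameters in the same way, by treatment group and scheduled post-baseline visit. It gives the overall normal/abnormal ECG assessment for every scheduled time-point. Protocol 9.4.3.4 says: "ECG parameters will be summarised by time-point including changes from baseline".

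**The concern.** Protocol Table 2 names hypotension as a risk. It reports falls of about 5 mmHg with zibotentan, usually without symptoms, and says that dapagliflozin may also lower blood pressure slightly. The Day 1 readings are the only scheduled blood pressure and ECG readings with a stated time after a dose. If the windowing rule is followed as written, they are neither baseline nor part of any analysis visit. The report would then specify no arm-level mean or mean change in blood pressure, pulse or QTcF at those times. Whether early haemodynamic and ECG effects are summarised would depend on how a programmer reads the text.

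**Working it through.** No sample size, alpha or estimate is involved. The check maps each scheduled time to Table 4 and then looks for any other summary that would pick up the unmapped readings.

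**Step 1: mapping.** Inputs are the visit days and allowances in the protocol's schedule of activities, the study-day rule in SAP 3.3.1.3 and the windows in SAP Table 4.

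| Reading | Study day (range) | Table 4 window |
|---|---|---|
| Vital signs at 60, 120, 180 min | 1 | none |
| ECG at 2 h | 1 | none |
| Visit 3 | 8 (5 to 11) | Week 1 (2 to 11) |
| Visit 4 | 15 (12 to 18) | Week 2 (12 to 18) |
| Visit 5 | 22 (19 to 25) | Week 3 (19 to 31) |
| Visit 6 | 43 (38 to 48) | Week 6 (32 to 50) |
| Visit 7 | 57 (54 to 60) | Week 8 (51 to 78) |

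Vital signs: 3 + 5 = 8 times after the first dose, 5 mapped. ECG: 1 + 5 = 6 times, 5 mapped. Visits 3 to 7 stay in their intended windows at both ends of the allowance, so the gap is confined to Day 1.

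**Step 2: amount of data.** With 22 x 3 = 66 participants, up to 66 x 3 = 198 vital-sign sets and 66 x 1 = 66 triplicate ECGs are unmapped. These are counts of readings, not a measure of bias.

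**Step 3: where the readings can still appear.**

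- *Supine blood pressure.* SAP 4.6.6.1 defines low as systolic below 95 or diastolic below 60 mmHg, and the all-observations rule should bring Day 1 values into the treatment-emergent counts. The time after dose is not shown.
- *A uniform fall of 5 mmHg.* This would cross the limits only in participants starting below 95 + 5 = 100 mmHg systolic or 60 + 5 = 65 mmHg diastolic, so these counts describe a small shift poorly.
- *Shift table.* SAP 4.6.6.2 goes from baseline to maximum only, so it cannot show a fall.
- *Standing blood pressure and pulse.* SAP 4.6.6.1 sets no abnormality criteria for either. Unless the redacted objective measurement in SAP 4.6.8.1 uses them, they appear only in listings.
- *ECG parameters.* The criteria in SAP Table 10, including QTcF increases above 30 and 60 ms, can pick up the 2-hour reading, but again without its timing.
- *ECG normal/abnormal.* This table is by scheduled time-point, and the 2-hour ECG is one.

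**Step 4: timing at later visits.** Schedule footnote p puts ECGs before vital signs and PK sampling. Protocol 8.3.2 places routine vital signs "prior to blood collection for laboratory tests with the participant resting in a supine position". Under protocol 4.1, participants at treatment visits "will provide a pre-dose blood sample for PK analysis and other lab samples before the intake of study intervention". Together these imply that the Visit 3 to 6 readings are taken before that day's dose. The schedule rows themselves give no time at those visits.

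**The case against.** The best defence has four parts.

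1. **Nothing says the readings are dropped.** SAP 3.3.1.1 bars them only from baseline. SAP section 2, which lists departures from the protocol, does not mention dropping ECG summaries by time-point. The text can therefore be called unclear rather than wrong. That is fair, but the stated windowing rule still leaves these readings without a row. The SAP does specify time-points or Day 1 where it wants them: PK is summarised by visit and time-point (4.2.6.4), and Table 5 starts fluid retention AEs at Day 1.
2. **The readings are used elsewhere.** This stands for supine blood pressure and ECG. A reader might infer that the readings are missing from every by-visit table, or that any conclusion would rest on trough values alone. The documents support neither. The ECG normal/abnormal table can include the 2-hour reading, and the treatment-emergent summaries draw on all observations. That later readings are at trough is also only an inference.
3. **Protocol 9.4.3.2 itself describes vital signs by scheduled post-baseline visit.** This stands, so the mismatch with the protocol concerns ECG only.
4. **The consequence is limited.** The key blood pressure endpoint is change to Week 6, there is no formal testing, and no document says that the Day 1 readings are meant to estimate a first-dose effect rather than to monitor individuals. All of this stands. It limits how serious the gap is but does not close it.

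**Conclusion.** The point holds as a gap in the specification of safety reporting. Three of 8 vital-sign times and 1 of 6 ECG times after the first dose have no place in the by-visit vital-sign and ECG-parameter tables. For ECG parameters this conflicts with protocol 9.4.3.4. What is missing is an observed mean and mean change by arm at the only times stated to be after a dose. The remaining summaries do not replace it, least of all for falls in pressure, standing pressure and pulse. No key estimate changes.

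The conclusion assumes that the 60, 120 and 180 minutes count from the first dose, as their place after a pre-dose entry indicates, and that the SAP is programmed as written. It does not depend on the Visit 3 to 6 readings being pre-dose.

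**What to change.** In SAP Table 4, or in SAP 4.6.6.2 and 4.6.7.2:

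- Add Day 1 post-dose analysis time-points: 60, 120 and 180 minutes for supine and standing blood pressure and pulse, and 2 hours for ECG parameters.
- Present observed value and change from the pre-dose baseline by arm at each.
- Give the number in each arm below the SAP's own supine limits (systolic below 95, diastolic below 60 mmHg) at these times.
- State that the ECG normal/abnormal table by scheduled time-point includes the 2-hour Day 1 ECG.

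The cost is SAP wording and two further tables on data already scheduled for collection. With these rows, mapping rises from 5 of 8 to 8 of 8 for vital signs and from 5 of 6 to 6 of 6 for ECG. Sample size, alpha and key estimates do not change, and no protocol amendment is needed.

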Screening Period of up to 3 weeks: The Screening Visit (Visit 1) will take place between 7 to 21 days before the Randomisation Visit (Visit 2) to confirm participant eligibility and collect baseline data. There must be at least 7 days between Visit 1 and Visit 2 to allow sufficient time for laboratory results to be examined. At the Randomisation Visit (Visit 2), eligibility criteria will be reassessed, safety laboratory data reverified, and participants will be provided digital devices to measure their body weight starting the first day after the Randomisation Visit and every day at home.

Treatment Period of 6 weeks: During the Treatment Period, participants will visit the study centre 5 times. At Visit 2, participants will be randomised and will receive the first dose of the study intervention. At each study visit during the treatment period (from Visit 3 till Visit 6) participants will receive the once daily dose at the study centre and will provide a pre-dose blood sample for PK analysis and other lab samples before the intake of study intervention. When not visiting the study centre the patients will take the once daily dose of study intervention at home.

Follow-up Period of 2 weeks: Participants will return to the study centre for follow-up assessments approximately 2 weeks after their planned last dose of study intervention (planned last dose is at Visit 6).

Disclosure Statement: This is a parallel-group, placebo-controlled study to evaluate the safety of zibotentan and zibotentan/dapagliflozin; the study is blinded to the participants, investigators, and Sponsor.

Number of Participants:

Approximately 22 eligible participants are planned to be randomised to each of the 3 treatment groups, for a total of up to 66 participants.

Note: “Enrolled” means a participant’s agreement to participate in a clinical study following completion of the informed consent process. Potential participants who are screened for the purpose of determining eligibility for the study but are not randomly assigned/assigned in the study, are considered “screen failures” unless otherwise specified by the protocol.

Study Arms and Duration:

Participants who meet the eligibility criteria and agree to participate will be randomised to one of the following treatment groups (22 participants per group). All participants will receive 1 capsule (zibotentan or matching placebo) and 1 tablet (dapagliflozin or matching placebo) at every dosing.

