Follow-up Period of 2 weeks: Participants will return to the study centre for follow-up assessments approximately 2 weeks after their planned last dose of study intervention (planned last dose is at Visit 6).

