8 STUDY ASSESSMENTS AND PROCEDURES

- Study procedures and their timing are summarised in the SoA ([Table 1](#)). Protocol waivers or exemptions are not allowed.
- Immediate safety concerns should be discussed with AstraZeneca immediately upon occurrence or awareness to determine if the participant should continue or discontinue study intervention.
- Adherence to the study design requirements, including those specified in the SoA ([Table 1](#)), is essential and required for study conduct.
- All screening evaluations must be completed and reviewed to confirm that potential participants meet all eligibility criteria. The investigator will maintain a screening log to record details of all participants screened and to confirm eligibility or record reasons for screening failure, as applicable.
- Procedures such as ECHO (to exclude valvular disease and/or significant cardiomyopathy as defined in Section [5.2](#)), clinical chemistry, and haematology conducted as part of the participant's routine clinical management and obtained before signing of the ICF may be utilised for screening purposes, provided the procedures met the protocol-specified criteria and were performed within the time frame defined in the SoA ([Table 1](#)).
- The maximum amount of blood collected from each participant over the duration of the study, including any extra assessments that may be required, will not exceed 165 mL. Repeat or unscheduled samples may be collected for safety reasons or for technical issues with the samples and may be tested at the local laboratory.
- A mobile software application, and associated website system, will provide digital support to participants from randomisation through to, and including, Follow-up. AstraZeneca will provide a handheld device to access the mobile software application. The system will provide participants and site study staff with information and tools relevant to the conduct of the study in accordance with this protocol. This will comprise of study intervention reminders, clinical visit reminders, PRO questionnaires, and educational content relating to the disease and medication. AstraZeneca (or those acting on behalf of AstraZeneca) will set up clinical sites and invite site staff to use the digital

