8.2.1.2 Electronic Scale Measurement of Body Weight

Body weight will be measured at the study centre at study visits. There will be safety monitoring of body weight from the home-based monitoring devices, or as an alternative, paper diaries can be used for capturing the information. A body weight change of **CCI** kg per **CCI** is regarded as a **CCI** weight change and needs to be followed up by the investigator.

The investigator will have direct access to the online data for their participants using digital

devices. If there is a significant weight gain, the investigator will contact the participant immediately and arrange a clinic visit to assess health status. Participants with paper diaries will be instructed to contact the study staff if there is a significant weight gain.

Participants will also be advised to self-monitor and contact the investigator with any concerns.

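### The closest-to-target rule in SAP 3.3.2 lets a result-triggered repeat replace an early scheduled reading; at Week 6 any later replacement falls after the planned last dose

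*SAP*

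**What the plan says.** SAP 3.3.2 brings every post-dose visit into the analysis windows: "All scheduled and unscheduled visits occurring the day after first dose or later (including Early Termination visit), will be mapped to an appropriate visit". Where a window holds several values, the choice is made by distance from the target: "if there is more than one value per subject within a visit window, the closest assessment to the target date is assigned". A tie goes to the earlier value. SAP 3.3.3, on unscheduled visits, only refers back to 3.3.2. In SAP Table 4 the Week 6 window runs from Day 32 to Day 50 with target Day 43.

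The protocol's Schedule of Activities allows ±3 days for Visits 3-5 and ±5 days for Visit 6, and the Synopsis states that the "planned last dose is at Visit 6". SAP 3.3.1.2 ends the planned treatment period on the date of Visit 6 and starts follow-up the next day, but Table 4 does not stop the Week 6 window there.

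The protocol provides for unscheduled readings in several places:
- **Liver tests.** Appendix E 3 has the investigator request a new central blood draw without delay when the potential Hy's Law identification criteria are met.
- **Safety samples.** Section 8: "Repeat or unscheduled samples may be collected for safety reasons or for technical issues with the samples". Section 8.3.5 adds further samples at the investigator's discretion.
- **ECGs.** Section 8.3.3 allows extra recordings after abnormal findings.
- **Weight.** Section 8.2.1.2, on home monitoring: "If there is a significant weight gain, the investigator will contact the participant immediately and arrange a clinic visit to assess health status".

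**The concern.** Choosing the value nearest the target is harmless when extra readings arise at random. Here many arise because of a result, so whether a second value exists depends on the first value or on the outcome itself. A high ALT at an early scheduled visit leads to a repeat. The repeat tends to be less extreme through regression to the mean and, at Week 6, because treatment has finished. If it lies nearer the target day, it becomes the analysed value.

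At stake are the by-visit analyses that use Table 4: the exploratory mixed models for AST/ALT (SAP 4.2.8), MELD where its components are redrawn, and the by-visit laboratory and ECG summaries. Office weight (key objectives 3 and 4, SAP 4.2.2) can also be affected, possibly in the opposite direction, because a clinic visit prompted by weight gain selects a high reading. Blood pressure (key objectives 9 and 10) is exposed only if unscheduled readings are actually taken.

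The treatment policy strategy in SAP 4.2 does not cover the Week 6 case, because reaching the planned end of treatment is not an intercurrent event.

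**Working it through.** The plan gives no figure to reproduce, so the rule was enumerated directly.

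**Inputs.** Targets and windows from SAP Table 4 (Week 1: target Day 8, window 2-11; Week 2: 15, 12-18; Week 3: 22, 19-31; Week 6: 43, 32-50). Permitted visit days from the Schedule of Activities (target ±3 for Visits 3-5; Days 38-48 for Visit 6). Ties go to the earlier value.

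**Rule.** Let the scheduled visit be on day s, the target T, and a repeat g days later. The repeat replaces the scheduled value if |s + g − T| < |s − T|. With d = T − s (days early), this is 0 < g < 2d. A visit on or after its target (d ≤ 0) cannot be displaced by a later repeat. A same-day repeat ties and loses, so at Week 6 every later reading that displaces Visit 6 falls after the Visit 6 date.

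**Week 6.**

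| Visit 6 on | d | Displaced by a repeat on | Days after planned last dose |
|---|---|---|---|
| Day 38 | 5 | Days 39-47 | 1-9 |
| Day 39 | 4 | Days 40-46 | 1-7 |
| Day 40 | 3 | Days 41-45 | 1-5 |
| Day 41 | 2 | Days 42-44 | 1-3 |
| Day 42 | 1 | Day 43 | 1 |
| Days 43-48 | ≤ 0 | none | – |

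This gives 9 + 7 + 5 + 3 + 1 = 25 day-pairs on 5 of 11 permitted days. In 8 + 6 + 4 + 2 + 0 = 20 of them the repeat is at least 2 days after Visit 6.

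**Weeks 1-3.** Displacement is possible on 3 of 7 permitted days, with 5 + 3 + 1 = 9 pairs at each week. The participant is then normally still on treatment.

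**Share of repeats that win,** assuming visit days spread evenly over the permitted window (count the values of d above g/2):

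| Gap g (days) | Visit 6 | Visits 3-5 |
|---|---|---|
| 2-3 | 4/11 = 36% | 2/7 = 29% |
| 4-5 | 3/11 = 27% | 1/7 = 14% |
| 6-7 | 2/11 = 18% | 0/7 = 0% |

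These shares apply to participants who have a repeat. They are not shares of all participants.

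**Weight.** An unscheduled reading before a late Visit 6 can also win. A weight-gain visit on Day 41 is 2 days from target and beats a Visit 6 on Day 46, which is 3 days away. That reading is on treatment but selected for being high.

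**Scale.** With about 22 participants per arm, one swapped value that differs by Δ moves the raw arm mean by Δ/22, or about 4.5% of Δ.

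**After the fix.** With the scheduled value given priority, the displacing pairs fall from 25 (Week 6) and 9 (each of Weeks 1-3) to 0.

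**The case against.** The rule is fixed in advance, blind to results, the same in every arm and has an explicit tie-break. Preferring the scheduled visit is partly a convention. This stands as far as it goes, but while the rule ignores results, the set of readings it chooses from does not.

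A reader might infer more than the documents support:
- **That the Week 6 blood-pressure effect will be materially diluted.** No visible text requires a return visit after an abnormal office reading, and each supine value is already the mean of three readings (Protocol 8.3.2). Any figure in mmHg would rest on an invented recall rate.
- **That body-water volumes are affected.** Protocol 8.2.1.3 places bioimpedance at the scheduled timepoints, and no unscheduled measurement is described.
- **That the eGFR repeat contributes at Week 6.** In Protocol 7.1 the confirmed low eGFR is a criterion for stopping study intervention, which gives little reason for a repeat after the planned last dose.
- **That every Week 6 replacement is meaningfully off drug.** Laboratory samples at treatment visits are taken before dosing, about 24 hours after the previous dose. A repeat the day after Visit 6 has much the same interval, and an instruction to repeat without delay points to short gaps.
- **That safety signals are lost.** The composites compare every observation with baseline (SAP 4.2.1.2, 4.2.4.2). Home weight and loop diuretics use Table 6. Summaries of extremes use all observations (SAP 3.3.2), so the maximum/minimum, shift and treatment-emergent outputs keep the abnormal value.

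**Conclusion.** The concern holds in a limited form. SAP 3.3.2 allows a result-triggered repeat to replace a scheduled reading taken before its target day. At Week 6, with Visit 6 on Days 38-42, any later replacing reading falls after the planned last dose. That follows from the documents without further assumption.

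Its practical reach is narrower. The one result-driven repeat that the protocol clearly requires is for liver tests. Discretionary safety samples and ECGs can be affected, as can office weight at visits prompted by home weight gain. Blood pressure is affected only if unscheduled readings are taken.

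The 36/27/18% and 29/14/0% shares assume evenly spread visit days and that a repeat exists. The documents do not say how many participants will have both an early visit and a repeat, so no bias in mmHg or U/L can be given. It is likely to be small: towards a smaller Week 6 change for liver tests, and possibly upward for weight. No hypothesis is tested. This is a cheap improvement to make before unblinding, not a threat to the trial's conclusions.

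**What to change.** Replace the selection rule in SAP 3.3.2 for Table 4 windows with wording to this effect:

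- Within a window, the valid assessment from the scheduled visit is used.
- An unscheduled assessment is used only if the scheduled one is missing or technically invalid, and then the one closest to the target day.
- If two scheduled assessments fall in one window, the one closest to the target day is used.
- For Week 6, no assessment after the date of Visit 6 is used when Visit 6 has a valid value.

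The exception for invalid samples is needed because Protocol Section 8 allows repeats for technical reasons; without it, a faulty scheduled value would beat its valid repeat. Keep all observations for the composites and extreme-value summaries, as now.

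The cost is a few lines of SAP text and a small programming condition. The downside is that a scheduled value a few days further from the target day will sometimes be used.
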